#### 3.2.5 Visit Window

For safety, time windows are defined for any presentations that summarise values by visit. The following conventions apply:

• For safety data study day reference is date of first dose of study treatment as Day 1, for PK the reference is the time of study treatment administration on the day PK blood

samples are taken, for efficacy and PRO data study day references date of randomisation as Day 1.

- The time windows are exhaustive so that data recorded at any timepoint has the potential to be summarised. Inclusion within the time window are based on the actual date and not the intended date of the visit.
- All unscheduled visit data have the potential to be included in the summaries.
- The window for the visits following baseline are constructed in such a way that the upper limit of the interval falls half way between the two visits (the lower limit of the first post-baseline visit is Day 2). If an even number of days exists between two consecutive visits then the upper limit will be taken as scheduled visit day + (duration between scheduled visits)/2. (i.e. don't apply the minus 1 day).
- Subjects may delay durvalumab dosing under certain circumstances.
  - Dosing may be delayed per the Dosing Modification and Toxicity Management Guidelines, due to either an immune or a non-immune-related AE.
  - If dosing must be delayed for reasons other than treatment-related toxicity, dosing will resume as soon as feasible.
  - Dosing intervals of subsequent cycles may be shortened as clinically feasible in order to gradually align treatment cycles with the schedule of tumour efficacy (RECIST) and PRO assessments.
- Visit windowing is done separately for each assessment based on the schedule of events specific to that assessment.
- Should Study Day be missing (due to partial dates), then visit is assigned to the nominal visit at which that assessment was recorded, and no windowing will be performed for that specific assessment.
- Visit windowing is conducted up to and including the "Last dose of study treatment" visit. That is, the "Last dose of study treatment" visit is reassigned to a scheduled visit based on the study day that visit occurred at.
- For summaries showing the maximum or minimum values, the maximum/minimum value recorded on treatment are used (regardless of where it falls in an interval).
- Listings display all values contributing to a time point for a subject.
- For visit based summaries, if there is more than one value per subject within a time window then the closest value to the scheduled visit date are summarised, or the earlier, in the event the values are equidistant from the nominal visit date. The listings highlight the value for the subject that contributed to the summary table, wherever feasible. In summaries of extreme values, all post baseline values collected are used including those collected at unscheduled visits regardless of whether or not the value is close to the scheduled visit date.
- For summaries at a subject level, all values are included, regardless of whether they appear in a corresponding visit based summary, when deriving a subject level statistic such as maximum.

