## 3.2.4 On-treatment

For the purposes of summarizing safety data assessed at visits, in addition to baseline data, only on-treatment data are included in the summary tables. On-treatment data is defined as data on/after the first dose of study treatment and with assessment date up to and including the date of last study treatment + 30 days (safety follow-up) for ceralasertib monotherapy or the date of last study treatment + 90 days (safety follow-up) for ceralasertib and durvalumab combination, and prior to the start of any subsequent anti-cancer therapy.

The on-treatment period therefore comprises of the treatment period (first administration of any study treatment to and including last day of administration of any study treatment) and the safety follow-up period (30 days after last administration for ceralasertib monotherapy or 90 days after last administration for ceralasertib and durvalumab combination), and prior to the start of any subsequent anti-cancer therapy.

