## **3.2.6** Handling of Unscheduled Visits

Unscheduled visits are included in the method of assigning data to scheduled visits described in the rules in Section 3.2.5above. Unscheduled visits are not included as a separate visit in the summary tables.

For summaries at patient level, such as of extreme values, all post-baseline values collected are used to derive a patient level statistic including those collected at unscheduled visits and regardless of whether they appear in the corresponding visit-based summary.

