#### 4.3.12.3.2 Presentation

The change in each laboratory parameter from baseline to each post-baseline visit are summarised graphically.

Laboratory abnormalities occurring from the start of IP administration to the last assessment on study are presented. Worst toxicity grade, rates of grade 3-4 toxicity, and grade shifts of 2 or more from baseline to the maximum grade are presented. Summaries indicating hyper- and hypo- directionality of change are produced, where appropriate. Laboratory parameters that cannot be graded via NCI CTCAE are summarised with frequencies of post-baseline laboratory values categorized as low (L), normal (N), or high (H) using laboratory normal ranges comparing to baseline. Listings are provided for all laboratory results.

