# 3.2.4 On-treatment

For the purposes of summarizing safety data assessed at visits, in addition to baseline data, only on-treatment data are included in the summary tables. On-treatment data is defined as data on/after the first dose of study treatment (including Cycle 0) and with assessment date up to and including the date of last study treatment + 90 days (safety follow-up), and prior to the start of any subsequent anti-cancer therapy.

For biomarker data the on-treatment assessment is strictly defined as Cycle 0 Day 7. The Cycle 0 Days 15 – Day 28 period will be defined as off-treatment.

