## 4.3.14.2 Adverse Events

## 4.3.14.2.1 Definitions and Derivations

The Medical Dictionary for Regulatory Activities (MedDRA) (version 25 or higher) is used to code the AEs. AEs are graded according to the National Cancer Institute Common Terminology Criteria for AEs (CTCAE) (version 5.0).

Treatment emergent adverse events (TEAEs) are all AEs which onset or worsen in severity following the first administration of IP in Cycle 0 within the duration of the treatment period, up to and including 30 days after the last dose of study treatment for ceralasertib monotherapy or 90 days after last dose of study treatment for ceralasertib and durvalumab combination. Worsening in severity is determined by comparison with the pre-treatment CTCAE grade of the AE recorded closest to the start of dosing.

AEs with a missing start time or where time is not collected, which occur on the same day as first IP administration, are reported as treatment emergent.

For rules on missing or partial dates, see Section 3.4.6.

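### The laboratory worst-grade tables run to the last assessment on study, which contradicts the SAP's own on-treatment rule for safety tables; several related sections leave the window open

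*SAP*

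**What the plan says.** **Main-study SAP, on-treatment rule.** For safety data assessed at visits, section 3.2.4 says that, besides baseline, "only on-treatment data are included in the summary tables". The window runs "up to and including the date of last study treatment + 30 days (safety follow-up) for ceralasertib monotherapy". For the combination the limit is 90 days. In both arms it also closes when a new anti-cancer therapy begins. One bullet of section 3.2.5 agrees: for summaries of maxima or minima, "the maximum/minimum value recorded on treatment are used (regardless of where it falls in an interval").

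**Main-study SAP, laboratory rule.** Section 4.3.12.3.2 gives its own period: "Laboratory abnormalities occurring from the start of IP administration to the last assessment on study are presented". The next sentence names the outputs: worst grade, Grade 3–4 rates, and shifts of two or more grades up to the maximum.

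**Main-study SAP, sections that give no end of window.** A later bullet of 3.2.5 says "In summaries of extreme values, all post baseline values collected are used including those collected at unscheduled visits", and 3.2.6 says "For summaries at patient level, such as of extreme values, all post-baseline values collected are used". Sections 4.3.12.3.1, 4.3.12.4.1 and 4.3.12.4.2 refer to the maximum post-baseline CTC grade, and the liver categories are likewise defined on post-baseline values. Section 4.3.12.4.2 uses both bases for urinalysis: the shift to worst result is on treatment, the maximum grade is post-baseline.

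**Sub-study SAP.** The laboratory and extreme-value wording is repeated. Its on-treatment period is the "date of last study treatment + 90 days (safety follow-up), and prior to the start of any subsequent anti-cancer therapy", for every subject. Its TEAE definition allows 30 days for ceralasertib alone or "90 days after last dose of study treatment for ceralasertib and durvalumab combination. Worsening in severity". The sentence ends there, with no cut-off at a new therapy.

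**The concern.** Worst grade, Grade 3–4 rates, grade shifts and liver categories are all driven by a subject's extreme value, so one late sample can decide the result. Two programmers could each follow this SAP faithfully and produce different tables, because no section says whether 3.2.4 or 4.3.12.3.2 takes precedence.

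The laboratory and adverse-event tables would also describe different periods. The main-study TEAE definition in 4.3.12.2.1 closes at 30 or 90 days and at a new anti-cancer therapy. A laboratory value taken after that point can enter the worst-grade table under 4.3.12.3.2, while an event first reported at the same time is not treatment-emergent. A reader comparing the two sets of tables would see a discrepancy produced by the windows alone.

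**Working it through.** The plan gives no figure to reproduce, so the check sets the rules side by side.

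| Place (main-study SAP) | End of window after last treatment | Closes at new anti-cancer therapy |
|---|---|---|
| 3.2.4, safety summary tables | 30 days (monotherapy), 90 days (combination) | Yes |
| 3.2.5, maximum/minimum bullet | On treatment | By reference to 3.2.4 |
| 4.3.12.2.1, TEAEs | 30 / 90 days | Yes |
| 4.3.12.4.2, urinalysis shift to worst | On treatment | By reference to 3.2.4 |
| 4.3.12.3.2, laboratory abnormalities | Last assessment on study | No |
| 3.2.5, extreme-value bullet; 3.2.6 | Not stated | Not stated |
| 4.3.12.3.1, 4.3.12.4.1 and 4.3.12.4.2, maximum grade; liver categories | Not stated | Not stated |

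**Which values are treated differently.** Let t be the sample date, L the date of last study treatment, w = 30 or 90 days, and S the start of a new therapy, if any.

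- Under 3.2.4, a post-baseline value counts if first dose ≤ t ≤ L + w and t < S.
- Under 4.3.12.3.2, it counts if first dose ≤ t ≤ last assessment on study.
- The rules disagree when t > L + w or t ≥ S.

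**Direction.** Every value that counts under 3.2.4 also counts under 4.3.12.3.2. A maximum over the larger set cannot be smaller, so the longer window leaves each subject's worst grade unchanged or raises it. The same holds for the Grade 3–4 rate and for upward shifts of two or more grades.

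**If sampling stopped at L + w.** The first disagreement (t > L + w) would vanish. The second would remain for S ≤ t ≤ L + w. That stretch can be up to 90 − 30 = 60 days longer in the combination arm.

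**Size.** This depends on how long laboratory samples are taken after last dose and on how many subjects start a new therapy while still sampled. The SAP states neither, so no estimate is possible from it.

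**Sub-study.** Visit-based safety tables end at 90 days and at a new therapy. TEAEs end at 30 or 90 days with no new-therapy cut. The two differ on both counts, and the main-study TEAE definition does contain the cut that is missing here.

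**The case against.** **The extreme-value sentences may only be about unscheduled visits.** This stands. The bullet in 3.2.5 goes on to say that closeness to the scheduled date does not matter, and 3.2.6 is headed as a rule for unscheduled visits. Read under 3.2.4, both can mean all on-treatment values, scheduled or not. A reader might infer that 3.2.5 and 3.2.6 also extend to the last assessment on study. They do not say so: only 4.3.12.3.2 states that end point, and the contradiction rests on that section against 3.2.4 and the maximum/minimum bullet.

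**Few values may be affected.** This stands as far as it goes. Sampling may stop with safety follow-up. A reader might infer that most subjects are affected because this population is expected to progress and switch therapy. The anticipated progression percentages are blacked out and no rate of later therapy is given, so that inference has no support here. But the new-therapy cut still separates the two rules inside the 30- or 90-day window.

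**No comparison is biased.** The safety sections describe summaries and no between-arm test, and laboratory grades are not attributed by cause. It would go too far to say that a safety comparison is biased or that late values are blamed on study drug. What remains is a descriptive table, shown by arm, whose window is contradictory.

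**On-treatment is not neutral either.** True: it is 30 days in one arm and 90 in the other. A longer window may also have been wanted to catch late toxicity. In that case the plan should say so and label it.

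**The sub-study's 30/90 split may be deliberate.** Plausible: every subject receives ceralasertib alone in Cycle 0, so someone who stops then has had monotherapy only. The split is not shown to be wrong. Only the missing new-therapy cut-off is a clear omission.

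**Conclusion.** The point holds as a contradiction within the main-study SAP. Section 4.3.12.3.2 sets a laboratory window that 3.2.4 and the maximum/minimum bullet of 3.2.5 exclude. The remaining extreme-value, maximum-grade and liver wording does not resolve the matter, and the urinalysis section mixes the two bases.

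The direction is known: the longer window can only leave worst grades unchanged or raise them. The size cannot be determined. Any effect requires laboratory samples taken after a new therapy starts, or beyond 30 or 90 days after last treatment. The primary endpoint is untouched. The matter concerns safety outputs and should be settled before programming is final.

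The sub-study SAP repeats the contradiction. In addition, its TEAE definition lacks the new-therapy cut-off, and its adverse-event and visit-based windows need reconciling.

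**What to change.** **Main-study SAP**

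- In 4.3.12.3.2, replace the end point of the laboratory-abnormality sentence with the on-treatment period of 3.2.4.
- In 3.2.5 (extreme-value and subject-level bullets), 3.2.6, 4.3.12.3.1 (including the liver categories), 4.3.12.4.1 and 4.3.12.4.2, state that extreme, maximum-grade, shift and liver summaries use all on-treatment values, scheduled or unscheduled.
- List later values, or show them in a separately labelled supportive table.
- Footnote the worst-value tables to say that the post-treatment window is 30 days for monotherapy and 90 days for the combination.

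**Sub-study SAP**

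- Make the same changes in 3.2.5, 3.2.6, 4.3.14.3.1, 4.3.14.3.2, 4.3.14.4.1 and 4.3.14.4.2.
- Add to the TEAE definition in 4.3.14.2.1 the new-therapy cut-off that the main-study TEAE definition and the sub-study's own 3.2.4 already contain.
- Reconcile the 30/90-day TEAE window with the 90-day window of 3.2.4. If the difference is intended, give the reason.

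**Cost.** SAP wording and one analysis flag; no design or endpoint change. The downside is that late values leave the main tables and the window stays unequal between arms. The listing or supportive table and the footnote keep both visible.

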## **3.2.6** Handling of Unscheduled Visits

Unscheduled visits are included in the method of assigning data to scheduled visits described in the rules in Section 3.2.5above. Unscheduled visits are not included as a separate visit in the summary tables.

For summaries at patient level, such as of extreme values, all post-baseline values collected are used to derive a patient level statistic including those collected at unscheduled visits and regardless of whether they appear in the corresponding visit-based summary.

## 3.2.7 Multiplicity/Multiple Comparisons

No adjustments for multiplicity are planned.

## 3.2.8 Missing Dates

Generally, the imputation of dates is used to decide if an observation is treatment emergent for adverse events (AEs) or concomitant medications. Flags are retained in the database indicating where any programmatic imputation has been applied, and in such cases, any imputed dates should not be used to calculate durations, where the results would be less accurate.

The following are the guidelines used when partial dates are detected in the study:

- For missing diagnostic dates (e.g. disease diagnosis), if day and/or month are missing use 01 and/or Jan. If year is missing, put the complete date to missing.
- For missing AE and concomitant medication start dates, the following is applied:
  - a. Missing day— impute the 1st of the month unless month is the same as month of the first dose of study drug then impute first dose date.
  - b. Missing day and month-- impute 1st January unless year is the same as first dose date then impute first dose date.
  - c. Completely missing— impute first dose date unless the end date suggests it could have started prior to this in which case impute the 1st January of the same year as the end date.
  - d. Imputed start date should be no later than the end date.
- For missing AE and concomitant medication end dates, the following is applied:
  - a. Missing day— impute the last day of the month unless month is the same as month of study discontinuation, then impute as study discontinuation date.
  - b. Missing day and month-- impute 31st December unless year is the same as year of study discontinuation then impute study discontinuation date.

- c. Completely Missing If an AE/medication has a completely missing end date then it is treated as ongoing, unless this is for a prior anti-cancer medication then impute the date of informed consent.
- If a subject are known to have died where only a partial death date is available then the date of death is imputed as the latest of the last date known to be alive +1 from the database and the death date using the available information provided:
  - a. For Missing day only using the  $1^{st}$  of the month.
  - b. For Missing day and Month using the 1st of January.

For patients with a treatment start date for ceralasertib, the following rules are applied for missing treatment end dates for ceralasertib:

- If start date of durvalumab is present, then impute the missing ceralasertib end date as start date of durvalumab.
- Otherwise if start date of durvalumab is missing, then impute the missing ceralasertib end date as min(start date of ceralasertib + 6 days, end of study date, DCO, date of investigator decision to stop ceralasertib).

For partial subsequent anti-cancer therapy dates, the following rules will be applied for missing start dates:

- Missing day: If the month is the same as treatment end date then impute to the day after treatment, otherwise first day of the month.
- Missing day and month: If year is the same as treatment end date then impute to the day after treatment, otherwise 1st January of the same year as anti-cancer therapy date.

For time to event endpoints, dropouts and missing data are handled according to the censoring rules detailed within the relevant sections for the endpoint.

Other rules for handling missing data are described under the derivation rules for that particular variable.

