#### **3.2.2** Study Treatment

The main study is a Phase 2, randomised, open-label, multicentre, international study assessing the efficacy and safety of ceralasertib and ceralasertib plus durvalumab in subjects with unresectable or advanced melanoma and primary or secondary resistance to programmed death-ligand 1 [PD-(L)1] inhibition. Approximately 150 subjects are randomised, at a 2:1 randomisation ratio (approximately 100 subjects in Arm 1 and approximately 50 subjects in Arm 2) to the following intervention groups:

- Arm 1: Ceralasertib 240 mg BD oral tablets, from Days 1 to 7 plus durvalumab 1500 mg Day 8, IV infusion, Q28D, until progressive disease, (confirmed RECIST 1.1-defined radiological progression), unacceptable toxicity, withdrawal of consent, or if a study treatment discontinuation criteria is met.
- 2. Arm 2: Ceralasertib 240 mg BD oral tablets, from Days 1 to 7, Q28D, until progressive disease, (confirmed RECIST 1.1-defined radiological progression), unacceptable toxicity, withdrawal of consent, or if a study treatment discontinuation criterion is met.

Crossover within the study is not be permitted. There is no defined maximum treatment duration for the treatment arms as the subjects receive study treatment until progressive disease (RECIST 1.1-defined radiological progression), unacceptable toxicity, withdrawal of consent, or if a study treatment discontinuation criterion is met.

Randomisation into the treatment arms is stratified by:

• Resistance to prior immune-oncology treatment (primary/early relapse in adjuvant setting vs secondary resistance).

• Baseline lactate dehydrogenase (LDH) expression (below and equal to the upper limit of normal vs above upper limit of normal).

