Dose intensity of study treatment(s) is addressed by considering relative dose intensity (RDI), where RDI is the percentage of the actual dose delivered relative to the intended dose through to treatment discontinuation. More specifically, RDI is defined as follows:

 $\circ$  RDI = 100% × d/D, where d is the actual cumulative dose delivered up to min(date of treatment discontinuation, date of death, data of DCO) and D is the intended cumulative dose up to the day of treatment discontinuation. D is the total dose that would be delivered, if there were no modification to dose or schedule.

Intended cumulative dose is calculated by summing the individual doses that should have been received up to and including the last day of study participation according to the planned dose and schedule.

This is given by the intended dose multiplied with the number of administrations that were planned to occur. These are different per treatment component.

- Intended cumulative dose of ceralasertib [mg] = daily dose × number of dosing days =•daily dose × [7 dosing days per number of complete cycles + dosing days of incomplete cycle]:
  - If  $mod_{28}(min(date of treatment discontinuation, date of DCO) date of first dose of ceralasertib + 1) ≤ 7 then:$

- Intended cumulative dose of ceralasertib = 240°mg × 2 × [7 × floor((min(date of treatment discontinuation, date of DCO) – date of first dose of ceralaserib +01)/28) + mod28(min(date of treatment discontinuation, date of DCO) – date of first dose of ceralasertib + 1)]
- Else if mod28(min(date of treatment discontinuation, date of DCO) date of first dose of ceralasertib + 1) > 7 then:
  - Intended cumulative dose of ceralasertib = 240 mg × 2 × [7 × floor(min(date of treatment discontinuation, date of DCO) – date of first dose of ceralasertib +o1)/28) + 7]
- Intended cumulative dose of durvalumab [mg] = dose × number of complete cycles = 1500°mg × ceil(min(date of treatment discontinuation, date of DCO) – date of first dose of durvalumab + 1)/28)

Note: ceil() refers to rounding up and floor() refers to rounding down to the next integer.  $mod_{28}(n)$  is the number n modulo 28.

Actual cumulative dose is calculated by summing all administered doses:

- ceralasertib dose = Actual dose recorded x actual frequency x duration
- durvalumab dose = Actual dose recorded

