• Impute the missing ceralasertib end date as min(start date of ceralasertib + 6 days, end of study date, DCO, date of investigator decision to stop ceralasertib, start date of durvalumab - 1 day)..

For partial subsequent anti-cancer therapy dates, the following rules will be applied for missing start dates:

• Missing day: If the month is the same as treatment end date then impute to the day after treatment, otherwise first day of the month.

• Missing day and month: If year is the same as treatment end date then impute to the day after treatment, otherwise 1st January of the same year as anti-cancer therapy date.

For time to event endpoints, dropouts and missing data are handled according to the censoring rules detailed within the relevant sections for the endpoint .

Other rules for handling missing data are described under the derivation rules for that particular variable

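### Main-study SAP imputes a missing ceralasertib end date as the durvalumab date with no upper bound, crediting at least 8 days to a 7-day course; Arm 2 and the sub-study use a bounded rule

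*SAP*

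**What the plan says.** **Imputation, main-study SAP, Section 3.2.8.** For a ceralasertib record with a start date but no end date there are two branches.
- Durvalumab date present: "If start date of durvalumab is present, then impute the missing ceralasertib end date as start date of durvalumab". Nothing else limits the date.
- Durvalumab date absent: "Otherwise if start date of durvalumab is missing, then impute the missing ceralasertib end date as min(start date of ceralasertib + 6 days", with end of study, data cut-off (DCO) and the investigator's decision to stop ceralasertib as the further bounds.

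**Schedule, main-study SAP, Section 3.2.2.** Arm 1: "Ceralasertib 240 mg BD oral tablets, from Days 1 to 7 plus durvalumab 1500 mg Day 8, IV infusion, Q28D". Arm 2: "Ceralasertib 240 mg BD oral tablets, from Days 1 to 7, Q28D". Section 3.2.5 adds: "Subjects may delay durvalumab dosing under certain circumstances".

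**Use of the dates, main-study SAP, Section 4.3.12.1.1.** Actual cumulative dose is built from "ceralasertib dose = Actual dose recorded x actual frequency x duration". The intended dose in the RDI counts 7 dosing days per complete 28-day cycle. Duration of exposure to ceralasertib runs to 21 days after the last non-zero dose, limited by death and DCO.

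**Imputation, sub-study SAP, Section 3.2.8.** There is one rule: "Impute the missing ceralasertib end date as min(start date of ceralasertib + 6 days, end of study date, DCO". The list of bounds continues with the investigator's stop decision and the day before durvalumab.

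**General caution, main-study SAP, opening of Section 3.2.8.** Imputed dates are flagged and are to be kept out of duration calculations where they would make the result less accurate.

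**The concern.** The first branch produces an end date on which no ceralasertib is planned. It can apply only to Arm 1 subjects who have a durvalumab date. Arm 2 has no durvalumab and always falls under the bounded branch, as do Arm 1 subjects with no durvalumab date. The same gap in the data is therefore filled differently in the two arms, and the Arm 1 error runs in one direction.

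The rule also ties the length of the ceralasertib course to the timing of another drug. Each day by which durvalumab slips in an affected cycle adds a day of ceralasertib. A recorded decision to stop ceralasertib limits the second branch but not the first.

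The text does not say which durvalumab date is meant. If it is the first infusion, a missing end date in a later cycle would be set before that cycle began.

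At stake are the descriptive summaries of ceralasertib exposure and dose intensity by arm.

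**Working it through.** The plan gives no figure for the effect, so its own formulas are applied.

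**Inputs**
- Planned daily dose: 240 mg × 2 = 480 mg; planned course 7 days per 28-day cycle (Sections 3.2.2 and 4.3.12.1.1).
- Durvalumab planned on Day 8 (Section 3.2.2), with delay allowed (Section 3.2.5).
- Assumptions, not in the documents: durvalumab on Day 15 (a 7-day delay); a stop decision on Day 4; six completed cycles with one missing end date; other doses as planned; and use of the imputed date in the derivations.

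**Check of the bounded rule.** Start + 6 days gives Day 7: 7 days × 480 mg = 3,360 mg. The intended dose for the cycle is also 7 × 480 = 3,360 mg, so the ratio is 100%. Duration of exposure for a single cycle is (7 + 21) − 1 + 1 = 28 days. The bounded branch agrees with the intended-dose formula and with the cycle length. The durvalumab formula, last dose + 20 days counted from the earliest dose of either drug, also gives 28 days from Day 8: (8 + 20) − 1 + 1 = 28.

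**One affected cycle under the first branch**

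| Durvalumab given | Imputed days | Credited dose | Share of cycle's intended dose | Duration of exposure if this is the last cycle, from that cycle's Day 1 |
|---|---|---|---|---|
| Day 8 (planned) | 8 | 8 × 480 = 3,840 mg | 8/7 = 114.3% | (8 + 21) − 1 + 1 = 29 days |
| Day 15 (assumed) | 15 | 15 × 480 = 7,200 mg | 15/7 = 214.3% | (15 + 21) − 1 + 1 = 36 days |
| Bounded rule, either case | 7 | 3,360 mg | 100% | 28 days |

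**Stop decision on Day 4 (assumed), durvalumab on Day 8.** The first branch credits 8 × 480 = 3,840 mg. A bounded rule that includes the stop decision credits 4 × 480 = 1,920 mg.

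**Subject level.** The SAP's RDI is cumulative. With K cycles, m of them affected and imputed length L:

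RDI = 100 × [(K − m) × 7 + m × L] / (7 × K)

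- K = 6, m = 1, L = 8: (35 + 8)/42 = 43/42 = 102.4%
- K = 6, m = 1, L = 15: (35 + 15)/42 = 50/42 = 119.0%
- All six affected: 114.3% or 214.3%

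**Duration of exposure.** Only the last non-zero dose enters the formula. A missing end date in an earlier cycle changes nothing. In the last cycle it adds one day with on-time durvalumab.

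**The case against.** The strongest reply is the caution that opens Section 3.2.8. If imputed dates are kept out of durations, none of the dose or exposure figures above arises. This stands in part: the SAP never states that imputed ceralasertib end dates feed exposure or RDI, so the effect is conditional. But the caution is general and qualified. Section 4.3.12.1.1 neither applies it to ceralasertib records nor gives a substitute duration, so a programmer could follow the rule straight into the dose calculation. Even with the caution applied, the imputed date itself remains implausible.

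Three further points stand.
- A reader might infer from 114% or 214% that Arm 1 RDI would be reported at those levels. The documents do not support that. These are single-cycle ratios, the RDI is cumulative per subject, and 214% also needs an assumed 7-day delay in the same cycle as the missing date.
- A reader might infer that the comparison of the arms on efficacy is affected. It is not: response, duration of response, progression-free survival and overall survival are not derived from ceralasertib end dates. The on-treatment safety window runs from the last administration of any study treatment, so it does not move when the imputed date equals that cycle's durvalumab date.
- The sub-study is non-randomised, has its own SAP and is not pooled with the main study for efficacy. Its different rule does not by itself make the main-study rule wrong. It does show that a bounded rule was written for the same Days 1 to 7 and Day 8 schedule, in a SAP dated three days later (15 against 12 March 2024).

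**Conclusion.** The concern holds as a defect in a stated rule. When a durvalumab date is present, the main-study SAP gives a ceralasertib end date at least one day beyond the planned course, with no upper limit and no regard to a stop decision. It does so only for Arm 1 subjects with a durvalumab date.

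The effect on reported results is conditional and probably modest. If imputed dates enter the derivations, an affected cycle is overstated by one day (14.3% of that cycle's intended dose) with on-time durvalumab, and by more with delay. The six-cycle example puts the subject's RDI at 102.4% to 119.0%, depending on the delay assumed. Duration of exposure moves only when the last ceralasertib record is the affected one. The number of records with a missing end date is unknown, so no arm-level bias can be stated. Only descriptive exposure and dose-intensity summaries are at risk.

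**What to change.** Reconcile Section 3.2.8 of the two SAPs. Replace both main-study branches with one rule for both arms: the imputed ceralasertib end date is the earliest of ceralasertib start + 6 days, end of study, DCO, the date of the decision to stop ceralasertib, and the same cycle's durvalumab date − 1 day (where there is one). The same-cycle restriction is an addition to the sub-study rule; it settles which durvalumab date is meant.

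Add a sentence to Section 4.3.12.1.1 stating whether imputed end dates enter duration of exposure, actual cumulative dose and RDI and, if not, what is used instead.

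This is a rule for analysis dates; no dosing instruction changes. With the bound in place, a missing end date gives at most 7 days, 3,360 mg and 100% of the cycle's intended dose in either arm, whether durvalumab is on time or late. The cost is a short text change and about one line of code. Where imputed dates are used, reported Arm 1 exposure will be slightly lower.
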